#### **4.2.3.3 Exposure**

All summaries of exposure will be presented by combined treatment group as well as by LTE treatment group for the full analysis set.

Summary statistics will be provided for the duration of exposure. Descriptive statistics including quartiles will be provided in addition to the number and percentage of subjects treated  $\geq 24$  weeks,  $\geq 52$  weeks (both for combined data from feeder and LTE study only),  $\geq 76$  weeks,  $\geq 104$  weeks,  $\geq 128$  weeks,  $\geq 156$  weeks,  $\geq 180$  weeks, and  $\geq 208$  weeks. Furthermore, the total treatment days and total subject-years of exposure will be presented.

The number and percentage of subjects with infusions (for combined data from feeder and LTE study) and infusions during LTE (for LTE study), respectively, will be presented by total number of infusion (i.e., 1, 2, 3, etc). For weeks 24 (for combined data from feeder and LTE study only) and all scheduled visits in the LTE study (including week 52/LTE Day 1), the number and percentage of subjects with infusion/ no infusion will also be presented.

Furthermore, the time to discontinuation of investigational product will be presented as Kaplan-Meier plot including the number of subjects at risk (ie, still on investigational product) at weeks 24, 52, 76, 104, 128, 156, 180, and 208. Subjects in the “Randomised Placebo” treatment group who switched to anifrolumab will be censored using the last infusion of placebo as the censoring date and in the All Anifrolumab treatment group (using the first infusion in the LTE as day of first infusion). In interim analyses subjects who did not discontinue IP or completed/withdrew from study will be censored using the last infusion as the censoring date.

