## 1.2 Study design

This is a Phase 3, multicentre, multinational, randomised, double-blind, placebo-controlled extension study characterising the long-term safety and tolerability of an IV treatment regimen of anifrolumab (300 mg) versus placebo in subjects with moderately to severely active systemic lupus erythematosus (SLE) who completed a Phase 3 study (D3461C00004 or D3461C00005) through the 52-week double-blind treatment period.

Approximately 575 subjects from Studies D3461C00004 or D3461C00005 (also referred to as the feeder studies) who were previously treated with anifrolumab (150 or 300 mg) or placebo for 52 weeks while receiving standard of care (SOC) treatment and who are willing to continue treatment may participate in the long-term extension (LTE) study if all eligibility criteria are met. Subjects will receive either a fixed IV dose of 300 mg anifrolumab every 4 weeks (Q4W) for up to 39 doses (LTE Week 0 to LTE Week 152) or placebo. Investigational product (IP) will be administered as an IV infusion via an infusion pump over a minimum of 30 minutes, Q4W.

In order to ensure that subjects with active SLE who enter the LTE will have adequate treatment of their disease in this 3-year blinded, placebo-controlled extension study, Investigators will be allowed to change the background SOC treatment for SLE during the course of the study. This LTE protocol allows for adding a new oral immunosuppressant or changing background immunosuppressants, as well as for flexible oral corticosteroids (OCS) use, so that subjects may achieve adequate control of their disease on study. However, it is recommended that subjects receive the lowest possible corticosteroid dose.

In the LTE study, treatment assignment will follow an Interactive Voice/Web Response System (IXRS) algorithm as follows:

- Subjects previously treated with anifrolumab 300 mg IV will stay on blinded treatment
- Subjects previously treated with anifrolumab 150 mg will switch to blinded anifrolumab 300 mg
- Subjects previously randomised to placebo will be re-randomised 1:1 to blinded anifrolumab 300 mg or placebo

Therefore, in the LTE study subjects will receive double-blind treatment with either anifrolumab 300 mg or placebo in an approximate ratio of 4:1.

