### **1.3 Number of subjects**

No formal comparisons are planned in this study; point estimates and confidence intervals (CIs) will be presented for each treatment group separately. The sample size is not based on statistical considerations, but is defined as all subjects who completed the treatment period in

the Phase 3 feeder Studies D3461C00004 or D3461C00005 (through Week 52) and met all study eligibility criteria. Assuming annual dropout rates of 30%, 30%, and 20% following placebo, anifrolumab 150 mg, and anifrolumab 300 mg, and that 90% of the subjects completing studies D3461C00004 or D3461C00005 enter the LTE, follow-up times of approximately 893, 517, and 1343 subject years for the “Randomised Anifrolumab 300 mg,” “Randomised Placebo,” and “All Anifrolumab” treatment groups are expected. Given this exposure, the 95% CIs for an AESI for which the observed incidence rate is 10 events in 1000 subject years will be 5.21 to 19.21 for “Randomised Anifrolumab 300 mg,” and 4.24 to 23.57 for “Randomised Placebo.” For an AESI for which the observed incidence rate is 1 event in 1000 subject years, the 95% CI will be 0.18 to 5.42 for “All Anifrolumab” (0.13 to 7.95 for “Randomised Anifrolumab 300 mg”), and 0.07 to 15.25 for “Randomised Placebo,” using the Rothman-Greenland Method ([Rothman and Greenland, 1998](#)).

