### 3.3.4 Exposure of investigational product

An infusion of IP is defined as follows:

- Start time and end time of study drug infusion are not missing and start time and end time are not equal, and
- Volume of infusion bag prior to infusion start is greater than volume of infusion bag at the end of infusion or investigator confirmed that study drug was administered according to protocol.

The duration of exposure to the investigational product per subject is defined as the number of days between the start and the end dates of investigational product plus the dosing frequency time:

For the subjects randomised to Placebo in the feeder study who switch to Anifrolumab, the following definition applies, to account for exposure time of the feeder study (placebo) up until the day before their first dose of Anifrolumab in the LTE study:

Duration of exposure (days) = ([first dose date in LTE-1]) – first dosing date in feeder study + 1,

For the All Anifrolumab group the following definition applies, to account only for their exposure time of Anifrolumab:

Duration of exposure (days) = (Last Anifrolumab dosing date + 28 days) – first Anifrolumab dosing date + 1,

For all other subjects, duration of exposure is defined as:

Duration of exposure (days) = (Last dosing date + 28 days) – first dosing date + 1.

Duration of LTE exposure is consequently defined as

Duration of LTE exposure (days) = (Last dosing date of LTE study + 28 days) – first dosing date of LTE study + 1.

The total subject years of exposure is the sum of duration of exposure (days) of all subjects in the respective treatment group divided by 365.25 (days/year).

The total number of infusions and infusions during LTE will be counted per subject.

The time to discontinuation of investigational product is the same as the duration of exposure.

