**Table 2 Visit windows**

Adjusted Defined Windows Visit	Scheduled Study Day	Maximum Windows
Baseline / Day 1	1	Study Day $\leq 1$
Week 24	169	$155 \leq \text{Study Day} \leq 182$
Week 52	365	$351 \leq \text{Study Day} \leq 378$ and LTE Study Day 1
Gap a	N/A	$379 \leq \text{Study Day} \leq \text{LTE Study Day 1}$
Week 56	29 in LTE study	$2 \leq \text{LTE Study Day} \leq 42$
Week 60	57 in LTE study	$43 \leq \text{LTE Study Day} \leq 70$
Week 64	85 in LTE study	$71 \leq \text{LTE Study Days} \leq 98$
...	...	...
Continue in 4-week intervals	Continue in 28-day intervals	Continue in 28-day intervals
...	...	...
Variables to be assessed/measured during follow-up		
Week 208	1092 in LTE study	$1079 \leq \text{LTE Study Days} \leq 1106$
Week 212 (8 weeks post-final dose)	1120 in LTE study	$1107 \leq \text{LTE Study Days} \leq 1134$
Week 216 (12 weeks post-final dose)	1148 in LTE study	$1135 \leq \text{LTE Study Days}$
Variables not to be assessed/measured during follow-up		
Week 208	1092 in LTE study	$1079 \leq \text{LTE Study Day}$

a. This visit window covers longer than expected gaps between the feeder study and the first dose date in the LTE. This visit window will only be used in listings.

For assignment of data to time points using the visit windows, study day will be defined as (Date of assessment – date of first administration of investigational product) +1. Using this definition, the day of first dose of investigational product will be Day 1 and the scheduled visit date of Week 24 will be study day 169 (=168+1), for example. Data captured in the Phase 3 feeder study falling in a visit window after Week 52 [REDACTED] captured in the Phase 3 feeder study falling in Week 52 visit window will not be considered for by-visit summaries. LTE Study Day is defined accordingly as (Date of assessment – date of first administration of investigational product in LTE study) +1. Data assessed at LTE Study Day 1 will be assigned to Week 52 visit window. Data captured in the LTE study after LTE Study Day 1 falling into a visit window before Week 56 will not be considered for by-visit summaries.

If multiple readings are recorded within a single visit window, the following rules will be followed:

- If there are 2 or more observations within the same visit window, then the non-missing one closest to the scheduled visit will be used in the analysis.

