### **4.2.3 Presentation of study population**

#### **4.2.3.1 Subject disposition**

Beside the summary of protocol deviations, all summaries of subject disposition will be presented by combined treatment group as well as by LTE treatment group for the full analysis sets.

The number and percentage of subjects with the following study outcomes will be summarised. In the presentation by LTE treatment group, the first 5 categories will not be presented.

- Completed the Phase 3 feeder studies up to and including Week 52 (Visit 14/EDV) and either enrolled to LTE, or completed 12 weeks of follow-up after their last dose of IP (Follow-up Visit 2, or Week 52 for subjects who prematurely discontinued IP > 12 weeks prior)
- Withdrew from the Phase 3 feeder studies including reason for withdrawal
- Completed treatment with investigational product in the Phase 3 feeder studies up to and including Week 48 (i.e., with last administration of investigational product at Visit 13)
- Permanently discontinued the treatment with investigational product in the Phase 3 feeder studies including reason for withdrawal
- Randomised to the LTE study
- Completed the LTE study up to and including Week 208 (LTE Visit 40/EDV)
- Withdrew from the LTE study including reason for withdrawal
- Completed treatment with investigational product in the LTE study up to and including Week 204 (LTE Week 152, ie, with last administration of investigational product at LTE Visit 39)
- Permanently discontinued the treatment with investigational product in the LTE study including reason for withdrawal

This summary will be repeated for the first 5 categories by feeder study (D3461C00004 and D3461C00005) and corresponding feeder study treatment group. The number and percentage of subjects randomised to the respective study as well as the randomised treatment in the LTE study will also be included in the summary by feeder study.

Furthermore, the number and percentage of subjects remaining on investigational product, discontinued investigational product but remain on study, and withdrawn from study will be summarised by 6-month intervals (i.e., at weeks 24, 52 [both for combined data from feeder and LTE study only], 76, 104, 128, 156, 180, and 204). This summary will be presented for all given time points even with less than 25 subjects.

A summary of number and percentage of subjects in each population will be provided.

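### The time-to-discontinuation Kaplan-Meier plot censors placebo switchers 28 days earlier than it times events, conflicts with SAP 3.3.4, and biases Randomised Placebo discontinuation upward around Week 52 by an amount that depends on an undefined event

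*SAP*

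**What the plan says.** SAP 3.3.4 defines the time scale: "The time to discontinuation of investigational product is the same as the duration of exposure". For most subjects that is "Duration of exposure (days) = (Last dosing date + 28 days) – first dosing date + 1". Placebo subjects who switch to anifrolumab have their own rule, which is "to account for exposure time of the feeder study (placebo) up until the day before their first dose of Anifrolumab in the LTE study".

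SAP 4.2.3.3 plans a Kaplan-Meier plot of this variable, with the number still on investigational product shown at Week 52 among other time points. For this plot, Randomised Placebo subjects who switch "will be censored using the last infusion of placebo as the censoring date". At interim analyses, subjects still on treatment are likewise censored at their last infusion, with no 28 days added. In the final analysis, switchers are the only subjects for whom the visible text names a censoring rule. It does not say whether a subject who completes feeder treatment and does not enter the LTE, or who completes the LTE, has an event or is censored.

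**The concern.** Two placebo subjects with the same last placebo dose at Week 48 are placed 28 days apart according to what happens next. If not entering the LTE counts as discontinuation, the non-entrant has an event at Day 365, while the switcher leaves the risk set at Day 337. Yet the switcher is known to have continued, because the switch takes place at LTE entry. Removing that subject early uses later status to shrink the denominator for any event between Days 338 and 365, so the censoring is informative.

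Of the two primary groups, only Randomised Placebo contains switchers, so the distortion is one-sided. What is at stake is the level of the placebo curve from about Week 52 onward and the at-risk count printed beneath it.

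**Working it through.** The plan gives no figure for this plot, so there is none to reproduce.

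**Inputs**
- Study day = 7 × week + 1 (SAP 4.1.2), so Week 44 = Day 309, Week 48 = Day 337 and Week 52 = Day 365.
- Last feeder dose at Week 48 (SAP 4.2.3.1). First LTE dose nominally at Week 52 (SAP 1.2).
- Placebo dropout, SAP 1.3: "Assuming annual dropout rates of 30%, 30%, and 20% following placebo, anifrolumab 150 mg, and anifrolumab 300 mg". The same section assumes that 90% of feeder completers enter the LTE.
- Switch share, SAP 1.2: "Subjects previously randomised to placebo will be re-randomised 1:1 to blinded anifrolumab 300 mg or placebo".
- Assumption made here: the 30% who drop out in Year 1 have their last dose by Week 44, so 70% remain just before Day 365.

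**Step 1: dates**
- Last dose Week 44: event at 309 + 28 = Day 337. This ties with the switchers' censoring, so they still count as at risk.
- Last dose Week 48: event at 337 + 28 = Day 365.
- Switcher, SAP 4.2.3.3: censored at Day 337.
- Switcher, SAP 3.3.4: exposure ends at 365 − 1 = Day 364.

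**Step 2: Week 52, if LTE non-entrants are events (per 1000 placebo subjects)**
- Completers 1000 × 0.70 = 700; entrants 700 × 0.90 = 630; switchers 315; staying on placebo 315; non-entrants 70.
- As written: the risk set at Day 365 is 700 − 315 = 385 and the drop is 70/385 = 18.2%. Retention is 0.70 × (1 − 0.182) = 57.3%, so discontinuation is 42.7%.
- Switchers censored at last infusion + 28 days: the drop is 70/700 = 10.0%. Retention is 0.70 × 0.90 = 63.0%, so discontinuation is 37.0%.
- Excess: 42.7 − 37.0 = 5.7 points.

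**Step 3: other entry rates, same reading**

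| LTE entry | Drop as written | Drop aligned | Discontinued as written | Discontinued aligned | Excess (points) |
|---|---|---|---|---|---|
| 95% | 35/367.5 = 9.5% | 35/700 = 5.0% | 36.7% | 33.5% | 3.2 |
| 90% | 70/385 = 18.2% | 70/700 = 10.0% | 42.7% | 37.0% | 5.7 |
| 80% | 140/420 = 33.3% | 140/700 = 20.0% | 53.3% | 44.0% | 9.3 |

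**Step 4: later times.** In a simulation of 60,000 subjects on the nominal schedule with 90% entry, discontinuation at Day 728 is 59.0% as written and 54.8% aligned (4.2 points). At Day 1092 it is 71.5% and 68.6% (2.9 points). The excess shrinks but does not vanish.

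**Step 5: if LTE non-entrants are censored.** The excess at Week 52 is 0 points on exact visit days and about 0.6 points with ±7-day visit variation (applying that window to feeder doses is an assumption). It is about 1.6 points if some of the 30% dropout falls after the Week 48 dose. No scenario gave an understatement.

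**Step 6: which date cures it (non-entrants as events, 90% entry).** The SAP 3.3.4 date does not cure it on the nominal schedule: Day 364 still precedes the Day 365 events, and simulated discontinuation stays at 42.8%. Last infusion + 28 days gives 37.0%, the same as if nobody had switched. With ±7-day variation the results are 43.3% as written, 39.3% with last infusion + 28 days, and 37.1% with no switch. The aligned rule then removes most of the excess but not all.

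**The case against.** The strongest objection is that the size rests on an event definition that the SAP does not give. SAP 4.2.3.1 lists "Completed treatment with investigational product in the Phase 3 feeder studies up to and including Week 48" as an outcome separate from permanent discontinuation, and a completer who declines the LTE fits the former. Reading everyone not named for censoring as an event would also make every LTE completer an event at last dose + 28 days. That would take the curves to zero at about Week 208, which can hardly be intended. This objection stands as to size: 5.7 points is conditional, and the effect may be close to nothing. It does not remove the conflict between the two sections or the 28-day mismatch, and the missing event definition is itself a gap.

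A reader might infer that the plan exaggerates anifrolumab's retention advantage. The documents do not support that as a demonstrated result. The bias within Randomised Placebo goes one way, but its size is open, and SAP 1.3 plans no formal comparison. SAP 4.2.3.3 also presents exposure by combined treatment group, which includes Placebo Feeder + Placebo LTE. That group has no switchers. On the inputs above, with half of the non-entrants pseudo-assigned to it, its Week 52 drop is 35/(315 + 35) = 10.0%, the aligned value.

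A reader might also infer that the protocol's commitment to summarise retention over time is defeated. It is not: SAP 4.2.3.1 separately tabulates subjects on drug, off drug but on study, and withdrawn at six-monthly points, without this censoring rule.

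**Conclusion.** The rule is wrong as written, with limited reach. SAP 3.3.4 and 4.2.3.3 give different end dates for the same switchers (Days 364 and 337), and neither matches the event clock (Day 365). On the nominal schedule all switchers are absent from the Week 52 at-risk count, although they continued on blinded placebo treatment up to the switch.

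The upward bias in Randomised Placebo discontinuation is material (Steps 2 to 4) only if LTE non-entrants are events; if they are censored it is negligible to small (Step 5). Both results rest on the planning rates for dropout and entry, not on observed data.

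It would be a mistake to carry this over to the primary safety results. The AESI and SAE rates use their own exposure and time-at-risk definitions in SAP 3.1.1, and this censoring rule does not enter them.

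**What to change.** Amend SAP 4.2.3.3 in three respects:

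1. Censor Randomised Placebo switchers at last placebo infusion + 28 days, the same clock as events. Apply the same rule at interim analyses to subjects still on treatment.
2. State in the same sentence whether feeder completers who do not enter the LTE, and subjects who complete LTE treatment, are events or are censored at last infusion + 28 days.
3. Reconcile SAP 3.3.4. The day before the first LTE dose can remain the end of exposure for subject-years, but the text should then say that the Kaplan-Meier plot uses a different end date for switchers. The statement that time to discontinuation equals duration of exposure needs that exception.

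The cost is about one sentence in SAP 4.2.3.3, a matching clarification in 3.3.4 and one programming line. No new data are needed.

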### **4.3 Subgroup analysis**

No subgroup analyses are planned for this study.

## **5. INTERIM ANALYSES**

Interim analyses may be performed based on regulatory or other requirements. Treatment allocation in the LTE study will become known to the Sponsor and staff and/or designated CRO. The blind will be maintained for the investigator, investigational site staff, and for the subject. Further details are described in a separate unblinding plan.

An interim analysis was performed at the time of the conclusion of the Phase 3 feeder studies (D3461C00004 or D3461C00005) and to support the 4-month safety update for the SLE IV submission..

## 6. CHANGES OF ANALYSIS FROM PROTOCOL

The definitions of the treatment groups for analyses were updated to clarify which data will be included in each group. The additional supportive treatment group Placebo Feeder + Placebo LTE during the LTE study only was removed. An additional analysis set was defined to cover the outputs for the LTE study only- Full Analysis Set- LTE Study. [REDACTED]

[REDACTED]

